GC4419 was studied in a Phase 1b/2a clinical study, GT-001 (NCT01921426, [Anderson, Sonis, et al. 2018](#)) and Phase 2b study, GT-201 (NCT02508389). In study GT-001, GC4419 was administered throughout the full 6- to 7-week course of chemo-radiotherapy (CRT) at doses of either 30 or 90 mg, Monday-Friday (M-F), and appeared to substantially reduce the duration, incidence, and overall severity (defined here as the incidence specifically of Grade 4) of severe OM compared with historical expectations (data are based on 43 evaluable subjects). Further, GC4419 did not appear to increase the known toxicity of the CRT regimen (IMRT plus concurrent cisplatin), nor did it appear to interfere with tumor response to CRT assessed through 1 year post therapy (for details see [Anderson, Sonis, et al. 2018](#) and the Investigator's Brochure). These results supported the design of the randomized, double-blind, placebo-controlled, Phase 2b study GT-201, with two GC4419 doses of 30 and 90 mg selected for comparison with placebo and administered 5 days/week. As in GT-001, patients eligible for GT-201 were required to have locally advanced squamous cell carcinoma of the oral cavity (OC) or oropharynx (OP), with their standard care calling for concurrent IMRT and cisplatin. Results from 223 randomized subjects indicated that GC4419 at daily dose of 90 mg resulted in statistically significant reduction on the primary endpoint, severe OM duration, for subjects on the 90 mg arm compared to placebo, as determined by the non-parametric Van Elteren test. The median duration of SOM, as defined in the protocol, was 1.5 days for subjects receiving 90 mg of GC4419 vs 19 days for subjects receiving placebo ( $p=0.024$ ). Also, the incidence of SOM during the IMRT treatment period was 43% for subjects receiving 90 mg of GC4419 vs 65% for subjects receiving placebo (nominal  $p$  value=0.009), a relative reduction of approximately 34%. The safety profile of GC4419 in combination with the IMRT/platinum regimen in GT-201 study was acceptable; safety results with both the 90 mg dose and the 30 mg dose were similar to those with placebo (Anderson et al, 2019). Two year follow up for standard tumor outcomes (progression-free survival, overall survival, local control, distant metastasis-free rate) did not vary among the three study arms (Anderson et al, 2020).

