#### Secondary Endpoints:

- Cumulative incidence of SOM, defined as any occurrence of WHO Grade 3-4 OM, from the first IMRT fraction through the end of the study treatment period (last day of IMRT)
- Cumulative incidence of WHO Grade 4 OM and days of Grade 4 OM from the first IMRT fraction through the end of the study treatment period (last day of IMRT)
- Cumulative incidence of SOM, and days of SOM, from the first IMRT fraction through two weeks after the end of IMRT.

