prior to concomitant chemoradiation are not eligible for this study, nor are people for whom chemotherapy and radiation are only to be administered sequentially, not in a concurrent regimen.

 Eligible patients will be scheduled to receive a continuous course IMRT delivered in single daily fractions of 2.0 to 2.2 Gy, five days per week (Monday through Friday), with a cumulative radiation dose of 60-72 Gy. Planned radiation treatment fields must include at least two oral sites (buccal mucosa, floor of mouth, tongue, soft palate) that are each planned to receive  $\geq$  50 cumulative Gy.

 The 7th dose of cisplatin will only be administered if the subject is on the 7-dose weekly cisplatin schedule (weekly cisplatin schedule may be 6 or 7 doses, depending on Investigator choice).

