## 10.3. Oral Mucositis Assessments

OM assessments will be completed at the Screening Visit (within 28 days of IMRT start), Baseline Visit, twice weekly (no less than two days apart) within each five-day IMRT treatment period and once weekly for four weeks following end of treatment.

The extent of subjects' OM will be assessed by a trained evaluator and scored using the WHO OM toxicity scoring scale ([Appendix 2](#)). All subjects must have an oral assessment on the last day of IMRT treatment. If a subject withdraws for any reason prior to the end of IMRT, a complete oral assessment should be done on that day.

Study site personnel will be provided with specific training and instructions regarding OM assessment performance, grading, and documentation. Designated trained study staff (oral evaluators) will conduct all assessments using a standardized and consistent method. To reduce inter-observer variability, the fewest possible number of evaluators should be involved in the assessments of each subject. The oral evaluators will use a Sponsor-provided headlamp for all oral assessments conducted for this study.

The WHO scale will be the measure for assessing OM. The assessment of the impact of OM on a subject's ability to eat is critical for accurate scoring of the WHO scale. Therefore, standardization of the assessment is very important. A third-party vendor will perform data quality management for all OM scoring. This process will be outlined in a separate study document.

In order to reduce variability in assessing food intake, the definitions for solids, liquids, and nothing by mouth are provided here:

- Solid foods are defined as foods that need to be chewed. Examples include meat, grains and vegetables.
- Liquids are defined as foods that take the shape of their container. Examples include fruit juices, soups, pureed foods, mashed potatoes, cooked cereals (oatmeal), baby food, Jell-O®, pudding, and ice cream.
- Nothing by mouth is defined as no eating or drinking, except enough liquid to allow for taking medications.

The WHO scoring scale is appended in [Appendix 2](#).

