## **10.7.2. Treatment Phase**

### **10.7.2.1. Prior to GC4419 Infusion**

Prior to receiving the first dose of GC4419 the following observations and procedures will be conducted for all subjects:

- Confirm continued subject eligibility by reviewing inclusion/exclusion criteria (IMRT Week 1 Day 1 only)
- Record/update medical conditions and illnesses that have occurred since the subject signed the ICF and record in medical history including a review of tobacco and alcohol use (Week 1 Day 1 only)

- Complete Physical Exam (Last Day of IMRT regimen or Early Termination Visit Only)
- Body Weight (Week 1 Day 1, once weekly during Treatment Phase, and Last Day of IMRT or Early Termination Visit)
- Vital signs to be obtained at Week 1 Day 1, once during Week 4 and once during Week 7 and any additional IMRT weeks, and Last Day of IMRT or Early Termination Visit to include temperature, systolic and diastolic blood pressures, heart rate and respiration rate

*On Day 1 (Week 1) and Day 22 (Week 4), blood pressure must be measured at the following times: 1) within 30 minutes prior to the pre-GC4419 PK draw, and 2) after GC4419 infusion, prior to standing and prior to the End of GC4419 Infusion PK draw.*

- ECOG Performance Status to be evaluated at Baseline Visit, once during Week 4 and once during Week 7
- Record BSA at Week 1 Day 1, and once during Weeks 4 and 7 for tri-weekly cisplatin dosing or once per week for subjects receiving weekly cisplatin.
- Conduct clinical tumor assessment per [Section 10.6.1](#) Last Day of IMRT regimen or Early Termination Visit Only)
- Ensure concomitant medications have been recorded from date of enrollment
- Ensure AEs have been recorded from date of enrollment
- OM assessment using the WHO OM toxicity scale ([Appendix 2](#)) beginning on Week 1 Day 1 and then twice weekly thereafter (no less than two days apart) within each 5-day IMRT period, and Last Day of IMRT or Early Termination Visit.
- Draw blood for clinical laboratory measurements per [Section 10.1.2](#) to include hematology profile and serum chemistry profile (Week 1 Day 1, Day 3, 4 or 5 and once per week thereafter through the last day of IMRT. *Note: If safety labs have not been drawn during the study week in which the last day of IMRT regimen/Early Termination Visit occur, then the clinical laboratory measurements should be collected at that time.*
- Urine Pregnancy Test on Week 1 Day 1 and Week 4 Day 1

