AEs and SAEs with onset dates on or after the date of enrollment through 30 days following the last dose of GC4419, IMRT or cisplatin (i.e. whichever occurs last) will be recorded on the CRF. All subjects with SAEs will be followed until the events resolve, stabilize, become chronic, the subject completes the study, or the subject is lost to follow-up.

 Ventricular rate and P-R, QRS, QT, and QTc intervals will be assessed and recorded at Screening.

All OM assessments must be performed by trained evaluators. The extent of the subject's OM will be scored using the WHO OM toxicity scale. OM assessments will be completed at the Screening Visit, at the Baseline Visit, twice weekly (no less than two days apart) within each 5-day IMRT period and on the last day of IMRT or Early Termination Visit. For Week 1, the first OM assessment will occur at the Baseline Visit and one additional OM assessment must occur at least two days later during the week. The extent of the subject's OM will be scored using the WHO OM toxicity scale. OM assessments should continue weekly for four weeks following the last day of IMRT (Day 7, Day 14, Day 21 and Day 28  $\pm 2$  calendar days).

Symptom Related Questionnaires to be completed by subjects prior to the OM assessment at W1D1, and then prior to the second OM assessment each week and 28 days ( $\pm 2$  calendar days) post end of treatment (EOT).

For a woman of childbearing potential, serum pregnancy test must be performed at the Screening Visit and at the Last Day of IMRT or Early Termination Visit.

Clinical laboratory measurements will be conducted at the Screening Visit, twice during Week 1 (once at the Baseline Visit and again on Day 3, 4 or 5), and once weekly from Week 2 through the last day of IMRT. Clinical laboratory measurements at these visits will include the hematology profile (hemoglobin, hematocrit, red blood cell count, white blood cell count with differential, and platelet count. Differential to include total neutrophils, lymphocytes, monocytes, eosinophils, and basophils) and chemistry profile (glucose, BUN, creatinine, sodium, potassium, calcium, albumin, total protein, total bilirubin, direct bilirubin, alkaline phosphatase, ALT (SGPT), AST (SGOT), chloride, phosphate, bicarbonate, magnesium).

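### Oral mucositis scoring during IMRT has a minimum spacing but no maximum, so compliant schedules differ in their chance of detecting SOM episodes of about 3 to 4 days (small effect, cheap to close)

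*Combined protocol and SAP*

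**What the plan says.** Three places carry the spacing rule. Section 10.3 requires scoring "twice weekly (no less than two days apart) within each five-day IMRT treatment period". Section 10.7.2.1 asks for a score on Week 1 Day 1 and "then twice weekly thereafter (no less than two days apart) within each 5-day IMRT period". Table 5 footnote 12 repeats it, "twice weekly (no less than two days apart) within each 5-day IMRT period", and adds that in Week 1, after Baseline, "one additional OM assessment must occur at least two days later during the week". The synopsis methodology and Section 6.2 say only that scoring is twice weekly, with no spacing at all.

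No section states a maximum interval, fixed weekdays or a constant weekday pattern. The fixed points are Baseline and the end of treatment: "All subjects must have an oral assessment on the last day of IMRT treatment".

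The secondary endpoints in Section 5.2 rest on these scores. SOM incidence counts any single Grade 3-4 score. A further endpoint is "Cumulative incidence of SOM, and days of SOM, from the first IMRT fraction through two weeks after the end of IMRT". Section 12.5 plans descriptive summaries only. The protocol does not say how days between scores are counted. Section 12.5.2 leaves missing scores and unknown resolution dates to a separate SAP, whose text is not in the document reviewed.

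**The concern.** A minimum without a maximum lets two compliant sites observe the same episode differently. One may see it and the other miss it, or both may see it and record different lengths. Because any occurrence counts, a missed episode can change a subject's SOM status. Section 11.2.4 excludes OM from AE reporting, so the AE record offers no second capture.

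The synopsis wants the OM results set beside North American and historical data and wants to confirm uniform scoring. Section 10.3 standardises evaluators, equipment and food definitions but not timing. With about 30 centers and up to 70 subjects (70/30, or about 2.3 per center), local scheduling habits need not average out. Subjects attend every weekday for infusion and IMRT, so even spacing is available without extra visits.

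**Working it through.** The plan states no figure to reproduce. The check lists what the rule allows and what follows for detection.

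**Inputs.** Two scores per week and a two-day minimum (Sections 10.3 and 10.7.2.1, footnote 12). IMRT Monday to Friday (Table 2, footnote 3). Day 1 then Day 3 is enough, from footnote 12's Week 1 sentence, so Mon/Wed complies. Assumption: episode onset is uniform over calendar days.

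**Step 1, allowed pairs.** Mon/Wed, Mon/Thu, Mon/Fri, Tue/Thu, Tue/Fri, Wed/Fri.

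**Step 2, gaps.** Within a week the gap is second day minus first day. Between weeks it is 7 + (first day of next week) - (second day of this week), with Mon = 0 to Fri = 4.
- Same pair every week: Mon/Wed, Tue/Thu and Wed/Fri give gaps of 2 and 5 days. Mon/Thu, Tue/Fri and Mon/Fri give 3 and 4.
- Pair changes between weeks: Mon/Wed then Wed/Fri gives 7 + 2 - 2 = 7 days. This is 1 of the 36 week-to-week pairings; another 4 of 36 give 6 days.
- Alternating Mon/Wed and Wed/Fri gives gaps of 2, 7, 2 and 3 days over 14 days.

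**Step 3, chance that an episode of L days is never scored.** In a gap of g days, the episode escapes if it starts after one score and ends before the next. Hence P(miss) = sum of max(0, g - L) / sum of g.

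| L (days) | Gaps 3, 4 | Gaps 2, 5 | Gaps 2, 7, 2, 3 |
|---|---|---|---|
| 1 | 5/7 = 71.4% | 5/7 = 71.4% | 10/14 = 71.4% |
| 2 | 3/7 = 42.9% | 3/7 = 42.9% | 6/14 = 42.9% |
| 3 | 1/7 = 14.3% | 2/7 = 28.6% | 4/14 = 28.6% |
| 4 | 0 | 1/7 = 14.3% | 3/14 = 21.4% |
| 5 | 0 | 0 | 2/14 = 14.3% |
| 6 | 0 | 0 | 1/14 = 7.1% |
| 7 or more | 0 | 0 | 0 |

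Among fixed pairs, the choice of weekdays changes detection only for 3- and 4-day episodes.

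**Step 4, recorded days.** The counting rule is not given, so two were tried on a true 10-day episode, over all onset days.
- First SOM score to next non-SOM score: 7 to 11 days (Mon/Thu), 7 to 14 (Mon/Wed), 5 to 14 (alternating). The mean is 10.0 in each.
- First to last SOM score, inclusive: means of 7.4, 6.9 and 6.3 days.

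For a true 21-day episode, the first rule records 21 days under either fixed pattern and 16 to 26 under the alternating one, again with mean 21.

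**Step 5, effect on the incidence estimate (illustration).** Suppose 30 of 70 subjects have SOM and 3 of those have only a single 3-day episode. The expected extra loss is 3 x (2/7 - 1/7) = 0.43 subject, or 0.43/70 = 0.6 percentage points. The 95% half-width is 1.96 x sqrt(0.43 x 0.57/70), about 12 points.

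**The case against.** The strongest objection is that few episodes fall in the affected range. Section 4.1.1 describes a predictable course that worsens as radiation accumulates, with SOM lasting a median of about 3 to 4 weeks among those who develop it without prevention. SOM that appears and clears within 3 or 4 days during IMRT may be uncommon, and the documents give no count. This stands, and it is why the effect is rated small.

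A reader might take the GT-201 result in Section 4.2 as evidence that short episodes dominate: "The median duration of SOM, as defined in the protocol, was 1.5 days for subjects receiving 90 mg of GC4419". It does not show that. The figure is stated for all subjects on that dose, and their SOM incidence during IMRT was 43%. The median therefore probably includes subjects with no SOM, although the GT-201 definition is not reproduced. Even if 1- and 2-day episodes were common, they are missed equally often under every pattern in the table.

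A second tempting reading is that 7-day gaps are typical. Nothing suggests that sites alternate pairs, and a site keeping one pair never exceeds 5 days. A third is that the comparison with North American data is compromised. The spacing rules of the earlier studies are not given, so this cannot be said.

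The two-day minimum could also be read as two clear days between scores. Only Mon/Thu, Mon/Fri and Tue/Fri would then comply, with a maximum gap of 5 days (Mon/Thu followed by Tue/Fri). Footnote 12's Week 1 sentence argues against that reading.

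Finally, a blanket 3-to-4-day rule would fail for a subject starting on a Wednesday, whose second score that week would fall at a weekend. Section 10.5 foresees mid- and late-week starts. This objection is right and shapes the fix.

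**Conclusion.** The point holds as a modest design weakness. As written, the rule permits poorer detection of 3- and 4-day SOM episodes than an equally cheap alternative: 29% against 14% missed at 3 days, and 14% to 21% against 0% at 4 days. These figures assume uniform onset and the reading that Mon/Wed complies.

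The documents do not support a claim that days of SOM are biased by weekday choice. Under one plausible counting rule the mean is unchanged and only individual values and spread vary; under another the mean shifts. The protocol does not settle which applies.

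The OM endpoints are secondary and descriptive, and the illustrated effect on incidence is well inside sampling error. This does not threaten the trial's conclusions. Priority: optional.

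**What to change.** In Section 10.3, Section 10.7.2.1 and Table 5 footnote 12, state that in full IMRT weeks consecutive OM scores are 3 to 4 days apart (Mon/Thu, Tue/Fri or Mon/Fri), with the same pattern each week for a given subject. The same-pattern clause is needed because Mon/Thu followed by Tue/Fri would still leave 5 days. Keep the last-day-of-IMRT score as an addition. Keep the current two-day minimum for partial weeks: mid- or late-week starts, holidays and treatment breaks. A partial first week costs little, since Section 4.1.1 puts median SOM onset at about 28 to 35 days.

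The cost is wording in three places and less freedom to schedule the oral evaluator. Visits and assessments do not increase, and the three retained pairs already comply with the present rule.

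The change does not reach the scores after IMRT that also feed days of SOM. Those are weekly with a window of 2 days either side (Section 10.7.3.1), so gaps can reach 7 + 2 = 9 days to the first visit and (14 + 2) - (7 - 2) = 11 days between the first two. The synopsis methodology instead describes twice-weekly scoring until 28 days after IMRT; that difference needs reconciling separately.

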## **APPENDIX 2. WORLD HEALTH ORGANIZATION (WHO) SCORE OF ORAL MUCOSITIS**

Grade	Scoring Criteria
Grade 0:	None
Grade 1:	Erythema and Soreness; No ulcers
Grade 2:	Ulcers; Able to eat a solid diet
Grade 3:	Ulcers; Requires a liquid diet
Grade 4:	Ulcers; Not able to tolerate a solid or liquid diet; Requires IV or tube feeding

### APPENDIX 3. PERFORMANCE STATUS CONVERSION

Performance Status Conversion: ECOG - Karnofsky			
ECOG		Karnofsky	
Score	Description	Score	Description
0	Fully active, able to carry on all pre-disease performances without restriction.	100	Normal, no complaints, no evidence of disease
		90	Able to carry on normal activity, minor signs or symptoms of disease.
1	Restricted in physically strenuous activity, but ambulatory and able to carry out work of a light or sedentary nature, office work	80	Normal activity with effort, some signs or symptoms of disease
		70	Cares for self, unable to carry on normal activity or do active work
2	Ambulatory and capable of all self-care, but unable to carry out any work activities; Up and about more than 50% of waking hours	60	Requires occasional assistance, but is able to care for most of his/her needs
		50	Requires considerable assistance and frequent medical care
3	Capable of only limited self-care, confined to bed or chair more than 50% of waking hours	40	Disabled, requires special care and assistance
		30	Severely disabled, hospitalization indicated; Death not imminent
4	Completely disabled; Cannot carry on any self-care; Totally confined to bed or chair	20	Very sick, hospital indicated, death not imminent
		10	Moribund, fatal processes progressing rapidly
5	Death	0	Death

**APPENDIX 4. NATIONAL CANCER INSTITUTE-COMMON  
TERMINOLOGY CRITERIA FOR ADVERSE EVENTS,  
VERSION 5.0**

See the following website link for the complete NCI-CTCAE Version 5.0:

[https://ctep.cancer.gov/protocolDevelopment/electronic\\_applications/docs/CTCAE\\_v5\\_Quick\\_Reference\\_8.5x11.pdf](https://ctep.cancer.gov/protocolDevelopment/electronic_applications/docs/CTCAE_v5_Quick_Reference_8.5x11.pdf)

## APPENDIX 5. RECOMMENDED REGIMENS FOR HIGH-RISK CHEMOTHERAPY-INDUCED NAUSEA AND VOMITING (CINV) PER ASCO AND MASCC GUIDELINES

*Note: Both ASCO and MASCC define single-agent IV cisplatin as a “high risk” regimen for CINV.*

**ASCO:** <http://ascopubs.org/doi/pdf/10.1200/JCO.2017.74.4789>

**Table 6: Antiemetic Dosing for Adults – High Risk (Cisplatin)**

Drug Class	Agent	Dose on Day of Chemotherapy	Dose(s) on Subsequent Days
NK 1 Receptor Antagonist	Aprepitant	125 mg oral	80 mg oral; days 2 and 3
	Fosaprepitant	150 mg IV	Day 1 only
	Netupitant-palonosetron	300 mg netupitant/0.5 mg palonosetron oral in single capsule (NEPA)	Day 1 only
	Rolapitant	180 mg oral	Day 1 only
5-HT 3 Receptor Antagonist	Granisetron	2 mg oral OR 1 mg OR 0.01 mg/kg IV OR 1 transdermal patch OR 10 mg SC	Day 1 only
	Ondansetron	8 mg oral twice daily OR 8 mg oral dissolving tablet twice daily OR three 8 mg oral soluble films OR 8 mg or 0.15 mg/kg IV	
	Palonosetron	0.50 mg oral OR 0.25 mg IV	
	Dolasetron	100 mg oral ONLY	
	Tropisetron	5 mg oral OR IV	
	Ramosetron	0.3 mg IV	
Corticosteroid if aprepitant is used*	Dexamethasone	12 mg oral OR IV	8 mg oral OR IV; once daily on days 2-4*
Corticosteroid if fosaprepitant is used*	Dexamethasone	12 mg oral OR IV	8 mg oral OR IV day 2; 8 mg oral OR IV twice daily on days 3-4*
Corticosteroid if netupitant-palonosetron is used*	Dexamethasone	12 mg oral OR IV	8 mg oral OR IV; once daily on days 2-4*

Corticosteroid if rolapitant is used	Dexamethasone	20 mg oral OR IV	8 mg oral OR IV; once daily on days 2-4
Olanzapine	Olanzapine	10 mg oral	10 mg oral on days 2-4

\*Presumes patients are receiving an NK1 antagonist. If they are not, the **dexamethasone dose should be adjusted** to 20 mg on day 1 and 16 mg on days 2-4.

*MASCC*: full updated guidelines may be found at: <http://www.mascc.org/antiemetic-guidelines> (2016)

For the prevention of non-AC highly emetogenic chemotherapy, a three-drug regimen including single doses of a 5-HT3 RA, dexamethasone and an NK1 RA (aprepitant, fosaprepitant, netupitant or rolapitant), given before chemotherapy is recommended. In patients receiving non-AC highly emetogenic chemotherapy treated with a combination of an NK1 RA, a 5-HT3 RA and dexamethasone to prevent acute nausea and vomiting, dexamethasone on days 2–4 is suggested to prevent delayed nausea and vomiting. If aprepitant 125 mg is used in day 1, then dexamethasone 8 mg x 1 (days 2-4) + aprepitant 80 mg x 1 (days 2-3) OR dexamethasone 8 mg x 2 (days 2-4) + metoclopramide 20 mg x 4 (days 2-4). Please note that this dosage of metoclopramide derives from a phase III study and some regulatory authorities like EMA now recommend a maximum 0.5 mg/kg total daily dose.

